## List of Abbreviations and Definition of Terms

AE	Adverse Event
AESI	Adverse event of special interest
ANA	Antinuclear antibody
ATC	Anatomical therapeutic chemical
AUC 0-12h	Area under the serum concentration-time curve (12 hours)
AUC 0-inf	Area under the serum concentration-time curve extrapolated to infinity
AUC 0-t	Area under the concentration-time curve from time 0 to last measurable concentration
AUMC	Area under the first moment curve
AVA	Anthrax vaccine adsorbed, BioThrax
BMI	Body mass index
CBER	Center for Biologics Evaluation and Research
CI	Confidence interval
cm	Centimeter
C max	Maximum observed serum concentration
CRO	Contract research organization
CSR	Clinical study report
C t	Last measurable concentration
CV	Coefficient of variation
d	Day(s)
dsDNA	Double-stranded deoxyribonucleic acid
DSMB	Data Safety Monitoring Board
█	█
ECG	Electrocardiogram
eCRF	Electronic case report form
EDC	Electronic data capture
e-diary	Electronic diary
ED 50	50% effective dilution
EWV	Early withdrawal visit
FDA	Food and Drug Administration
FSH	Follicle-stimulating hormone

GCP	Good Clinical Practice
GMT	Geometric mean titer
HBV	Hepatitis B virus
HCV	Hepatitis C virus
HIV	Human immunodeficiency virus
hr	Hour
ICF	Informed consent form
ICH	International Conference on Harmonisation
ID	Identification, as in subject identification (number)
IM	Intramuscular
IP	Investigational product
IRB	Institutional Review Board
ITT	Intent-to-treat
$K_{el}$	Apparent elimination rate constant
kg	Kilogram
LLOQ	Lower limit of quantification
LOD	Limit of detection
MedDRA	Medical Dictionary for Regulatory Activities
min	Minute
MRT	Mean residence time
NF 50	50% neutralization factor
NOSTASOT	No Statistical Significance Of Trend
PE	Physical examination
PI	Principal Investigator
PK	Pharmacokinetic(s)
po	Per os (orally)
q 12 hr	Every 12 hours
RF	Rheumatoid factor
SAE	Serious adverse event
SAP	Statistical analysis plan
SC	Subcutaneous

SD	Standard deviation
SOC	System organ class
t 1/2	Half-life
TEAE	Treatment emergent adverse event
TLF	Tables, listings, and figures
t max	Time to maximum observed serum concentration
TNA	Toxin neutralizing antibody
TOST	Two one-sided t-tests
TSH	Thyroid stimulating hormone
UPT	Urine pregnancy test
US	United States
WHO	World Health Organization

## 1 INTRODUCTION

This Statistical Analysis Plan (SAP) is based on Protocol EBS.AVA.210 “A Phase 2 Drug-Vaccine Interaction Study to Examine Whether Co-administering AV7909 with Ciprofloxacin or Doxycycline Affects Antibiotic Pharmacokinetics or AV7909 Immunogenicity in Healthy Adults” (Version 3.0, 28 October 2019). This document specifies details of the definitions of the derived variables, analysis methods, assumptions and data handling conventions for the analyses of pharmacokinetics, immunogenicity and safety to be included in the clinical study report (CSR).

## 2 PROTOCOL SUMMARY

### 2.1. Study Objectives

#### 2.1.1 Primary Objective

To evaluate the pharmacokinetic (PK) profiles of ciprofloxacin or doxycycline when administered orally, prior to, and following, the intramuscular (IM) administration of a two-dose schedule of AV7909 administered two weeks apart.

#### 2.1.2 Secondary Objectives

- To assess the safety of concurrent administration of oral ciprofloxacin or doxycycline and two doses of AV7909 administered IM.
- To evaluate the Day 37 immune response using the toxin neutralizing antibody (TNA) assay following two IM doses of AV7909 with and without the concurrent oral administration of ciprofloxacin or doxycycline.

### 2.2 Study Design and Conduct

#### 2.2.1 Overall Study Design

This is a randomized, open-label, phase 2, multicenter trial to investigate the potential interactions of AV7909 and ciprofloxacin or doxycycline when administered concomitantly.

Healthy males and females 18 to 45 years of age, inclusive, will read, sign and date an informed consent form (ICF) and then be screened (2 to 28 days prior to randomization) for eligibility to participate in the study. Participants (N=210) meeting the entry criteria will be evenly randomized 1:1:1 to one of the three investigational product (IP) groups shown in **Table 1**. Approximately the first 40 participants who are randomized for either IP Groups 1 and 2 will be assigned to Treatment Groups 1A or 2A while the remaining 30 participants randomized into IP Groups 1 and 2 thereafter will be assigned to Treatment Groups 1B or 2B.

Randomization will be stratified by site. A representative racial distribution will be sought among participants and sites will be asked to recruit populations that are gender- and age-balanced (i.e., between 40-60% male with 40-60% of participants in the two age ranges of 18 to 30 years of age and 31 to 45 years of age).

**Table 1 Study Groups**

IP Group	Treatment Group	Treatment	Sample Size (N)	
1 Cipro	1A	AV7909 + ciprofloxacin (with PK assessment)	≈40	≈70
	1B	AV7909 + ciprofloxacin (without PK assessment)	30	
2 Doxy	2A	AV7909 + doxycycline (with PK assessment)	≈40	≈70
	2B	AV7909 + doxycycline (without PK assessment)	30	
3 AV7909	3	AV7909 only	70	
		TOTAL	≈210	

[figure not shown]
**Figure 1** shows the design for this study.

Ciprofloxacin (500 mg by mouth [per os] every 12 hours [q 12 hr]) will be administered to Group 1 on Days 4-9, Days 22-24 and Days 31-37, and doxycycline (100 mg by mouth [per os] every 12 hours [po q 12 hr]) will be administered to Group 2 on Days 2-9, Days 22-24, and Days 32-38.

All participants, including the 70 participants in Group 3, will receive AV7909 (0.5 mL) IM in the deltoid muscle on Days 8 and 23. For Groups 1A and 2A, the first vaccination will occur following completion of the PK sessions and after administration of the evening antibiotic (ciprofloxacin or doxycycline) dose.

An event schematic for this study is provided in **Figure 2**.

**Figure 1 Study Design for EBS.AVA.210**

[figure not shown]

cipro = ciprofloxacin; doxy = doxycycline; PK = pharmacokinetics; po = per os, (oral); q12 h = every 12 hours; TNA = toxin-neutralizing antibody; TSH = thyroid-stimulating hormone

aIn Group 1, the evening dose on Day 37 is not administered. bAntibiotic dosing for Groups 1 & 2 up to Day 8 is to enable 2 PK sessions prior to vaccination #1 (vac #1) on Day 8. Dosing continues on Day 9, extends around vac #2 (on Days 22 to 24) and then discontinues until Day 31 (cipro) or Day 32 (doxy). Cipro dosing continues from Day 31 to Day 37 and doxy dosing continues from Day 32 to Day 38, encompassing 2 PK sessions after the complete vaccination regimen as well as the blood draw for TNA. cSolid lines at Days 1, 8, 23, 37 and 51 are days when all groups have in-clinic visits. Days in red are those when Groups 1A and/or 2A have clinic visits for blood draws for pre-dose, trough values or PK.

All visits are performed on an outpatient basis, except Groups 1A and 2A participants will be admitted to the clinic in the evening for an overnight stay on days preceding serial (all day) blood collections needed for determination of cipro or doxy concentrations. For Group 1A, those samples will be taken on Days 4, 8, 31, and 35; for Group 2A, those samples will be taken on Day 2, 8, 32, and 38. AV7909 vac #1 will be administered to all groups on Day 8. For Groups 1B, 2B, and 3, it will be their first clinic visit after randomization and for Groups 1A and 2A, vaccination will occur in the evening following the second PK session. AV7909 vac #2 will be administered on Day 23. The final blood draw for TNA will be on Day 37 for all groups. There will be a final visit for safety for all groups on Day 51, four weeks after the last dose of AV7909, which is when the final blood draw for TSH & autoantibodies will also be collected.

**Figure 2 Event Schematic for EBS.AVA.210 Groups 1 to 3**

**AD** = Active days, ie, days where participants in one or more groups are being administered or taking IP or having site visits; \* \* \* line = days where the only participant activity should be diary entry. AE = Adverse event; AESI = Adverse events of special interest; ● = participants in Group 1A come to clinic for overnight stays; ● = participants in Group 2A come to clinic for overnight stays; Doxy = doxycycline; PK = pharmacokinetics; SAE = serious adverse event; TNA = toxin neutralizing antibody; TSH = thyroid stimulating hormone; X = day of randomization.

**Group 1A** = AV7909 + cipro (w/PK), N=40 planned; **Group 1B** = AV7909 + cipro (w/o PK), N=30 planned; **Group 2A** = AV7909 + doxy (w/PK), N=40 planned; **Group 2B** = AV7909 + doxy (w/o PK), N=30 planned; **Group 3** = AV7909 only, N=70 planned. ◆ = AM clinic visit, Group 1A; ◆ = AM clinic visit, Group 2A; ▲ = PK session, Group 1A; ▲ = PK session, Group 2A.

 (V) = Cipro doses administered in clinic. (H) = Cipro doses self-administered at home.  (V) = Doxy doses administered in clinic. (H) = Doxy doses self-administered at home.

 (V) = AV7909 vaccine administration on Days 8 and 23.  (★) = Clinic visit, all groups, for TNA blood draw.  (W) = Clinic visit, all groups, includes safety labs and blood draw for TSH & autoantibodies.

 The electronic diary starts with the first dose of investigational product which is on Day 4 for Cipro (Group 1 (◆)), on Day 2 for Doxy (Group 2 (◆)) and on Day 8 for AV7909 (Group 3 (◆)).

◆ = provisional blood draws if warranted upon participant report of possible AESI.

◆ = Safety visit for all groups; ◆ = Safety visit for doxy and cipro PK groups; ◆ = Safety visit only for doxy PK group; ◆ = Safety visit only for cipro PK group.

### 2.2.2 PK Sampling

Serial PK assessments will be conducted on the following days:

- Group 1A (ciprofloxacin): Days 4, 8, 31, and 35;
- Group 2A (doxycycline): Days 2, 8, 32, and 38.

On these serial PK assessment days, blood samples for measurement of drug concentrations will be collected at 0.25, 0.5, 0.75, 1, 1.5, 2, 2.5, 3, 4, 5, 6, 8, 10, and 12 hours post dose ( $\pm 5$  min through hr 4 then  $\pm 15$  min).

In addition, antibiotic pre-dose or trough values will be measured prior to the antibiotic's morning doses on the following days:

- Group 1A (ciprofloxacin): Days 4, 5, 6, 7, and 8, and on Days 31, 32, 33, 34, and 35;
- Group 2A (doxycycline): Days 2, 3, 4, 5, 6, 7, and 8, and on Days 32, 33, 34, 35, 36, 37, and 38.

### 2.2.3 Immunogenicity Assessment

For all participants, blood draws for TNA assessments will be done at randomization (Day 1) and on Day 37 ( $\pm 1$  day) (2 weeks following the final dose of a two-dose vaccination series). All immunogenicity laboratory samples will be evaluated using a validated TNA assay by Battelle Memorial Institute (Columbus, Ohio). Specific procedures related to collection, processing storage, and shipment of the samples will be provided in study-specific Laboratory Manual.

### 2.2.4 Safety Assessments

#### 2.2.4.1 Adverse Events

AEs (including SAEs and potential AESIs) will be recorded on the AE eCRF if they occurred from the time of the first administration of any study treatment (Day 2 for Group 2, Day 4 for Groups 1 or Day 8 for Group 3) through Day 51 or EWV. From the signing of the ICF until immediately before the administration of their first study treatment, only AEs resulting from a study-related procedure will be recorded on the AE eCRF. After Day 51 and through the 12-month safety follow-up, AEs, SAEs and AEs assessed by the DSMB to be of autoimmune etiology, i.e., AESIs, will be recorded on the AE eCRF.

Safety follow-up phone contacts to collect information on AEs, SAEs and AESIs will occur at 3 months (Day 114  $\pm 14$  days), 6 months (Day 205  $\pm 14$  days), 9 months (Day 296  $\pm 14$  days), and 12 months (Day 388  $\pm 14$  days) after the last scheduled vaccination.

Refer to Protocol EBS.AVA.210, [Section 9.2](#) for reporting adverse events.

#### 2.2.4.2 Clinical Laboratory Tests

All analytes to be tested during screening/safety/autoimmunity clinical laboratory tests are specified in Protocol EBS.AVA.210, [Table 10](#).

The following assessments will be performed at Screening only:

- Urine drug screen
- Serologic testing (HIV-1/HIV-2 antibodies, HBV surface antigen, and HCV antibody).
- Follicle-stimulating hormone (FSH) test in postmenopausal women.

Pregnancy testing will be performed at Screening, immediately following group assignment, before each vaccination, and at the Day 51 Final Study Visit or the EWV.

Blood and urine samples for safety clinical laboratory testing (hematology, serum chemistry, urinalysis) will be collected at Screening and Day 51 as well as at the EWV if the EWV occurs before Day 51.

Blood samples for TSH & autoantibody assessment of ANA, RF and anti-dsDNA will be taken at Day 1 after randomization, Day 51 or EWV or an unscheduled visit if the participant has received at least one dose of vaccine, and at the time of safety follow-up phone contact(s) if warranted from participant report(s) of a potential AESI. These samples will be shipped to the central laboratory and will be banked; testing for TSH and ANA, RF and anti-dsDNA autoantibodies will be performed only if medically indicated (as per PI's discretion).

All samples for testing will be sent to the central laboratory for analysis, except urine for pregnancy testing, which will be performed at the site and results documented in the eCRF.

Refer to Protocol EBS.AVA.210, [Section 8.3.2](#) for details on clinical laboratory tests.

#### **2.2.4.3 Physical Examination (PE)**

Complete PEs will be performed at Screening, the Final Study Visit (Day 51) and EWV, if applicable.

Symptom-directed PEs will be performed at all visits except the Screening and Final Study Visit and early withdrawal (including any unscheduled visits), only if required (ie, in response to the report/collection of AEs/SAEs/potential AESIs.)

Refer to Protocol EBS.AVA.210, [Section 8.3.3](#) for details on physical exams.

#### **2.2.4.4 Vital Signs**

Vital signs including seated/semi-recumbent systolic and diastolic blood pressure, heart rate, respiration rate, and temperature will be obtained at Screening and each subsequent clinic visit through Day 51/EWV(except at AM and PM clinic visits for groups 1A and 2A, and at Day 37 for all groups), including unscheduled visits. Height and weight will only be recorded at Screening. On vaccination days (Days 8 and 23), vital signs will be assessed prior to vaccination and at 30 ± 5 minutes post-vaccination.

Refer to Protocol EBS.AVA.210, [Section 8.3.4](#) for details on vital signs.

#### **2.2.4.5 E-diary**

Participants will be asked to fill out an electronic diary (e-diary) daily for postvaccination reactogenicity events (all groups) and an e-diary for antibiotic compliance (Groups 1 and 2). There are separate e-diary requirements for this study depending on the treatment group:

- Participants in all three groups will be required to fill out e-diary to capture reactogenicity events after each vaccination.
- Participants in Group 1 and Group 2 will be required to also fill out a separate e-diary to capture antibiotic compliance.

The e-diary to capture reactogenicity events post vaccination will collect the following information:

- each participant's daily oral temperature at the same time each day
- local injection site and systemic reactogenicity responses
- whether they have use of any medications (e.g., acetaminophen, aspirin, ibuprofen)

Refer to Protocol EBS.AVA.210, [Section 8.3.5.1](#) for details on the e-diary and severity grading of reactogenicity responses.

#### 2.2.4.6 Concomitant Medications

Prior and concomitant medication information (medications used 30 days prior to Screening or medications used since the last study visit) will be recorded at screening, randomization and at each study visit in the eCRF. Participants will also record concomitant medications taken in their e-diaries and site staff will review this information on a routine basis and with the participant at each study visit, transferring information to the concomitant medications eCRF page as appropriate intervals.

For the purposes of this trial, concomitant medications include prescription drugs and biologics, over-the-counter drugs as well as herbal and nutritional supplements.

### 2.3 Study Endpoints and Statistical Hypotheses

#### 2.3.1 Primary Endpoints

The two primary endpoints in this study, whether co-administration of AV7909 with antibiotics affects antibiotic PK profiles for ciprofloxacin or doxycycline, are evaluated separately with independent study subjects (Group 1A for ciprofloxacin, Group 2A for doxycycline).

For each of the primary endpoints, the equivalence tests on PK parameters ( $AUC_{0-12h}$  and  $C_{max}$ ) at steady state pre- and post-vaccination will be performed.

Specifically, for each antibiotic, the null hypotheses are:

- $AUC_{0-12h}$ : The geometric mean of the within-participant ratios of post-vaccination (Day 35 for ciprofloxacin and Day 38 for doxycycline) over the pre-vaccination (Day 8)  $AUC_{0-12h}$  is greater than 1.25 or less than 0.80.
- $C_{max}$ : The geometric mean of the within-participant ratios of post-vaccination (Day 35 for ciprofloxacin and Day 38 for doxycycline) over the pre-vaccination (Day 8)  $C_{max}$  is greater than 1.25 or less than 0.80.

The null hypothesis will be rejected when the 90% CIs of the geometric mean of the within-participant ratios is contained entirely within the equivalence bounds of [0.80, 1.25]. For each

antibiotic, to conclude that administration of two-dose regimen of AV7909 does not affect the steady-state PK profile, the null hypotheses should be rejected for both PK parameters  $AUC_{0-12h}$  and  $C_{max}$ .

## 2.3.2 Secondary Endpoints

### 2.3.2.1 Secondary Safety Endpoints

- Incidences of AEs from the first dose of any IP through the Final Study Visit (Day 51)
- Incidences of serious AEs (SAEs) from the first dose of any IP until the 12-month follow-up (Day 388)
- Incidences of solicited systemic and injection site reactions reported in participant e-diaries following each vaccination
- Incidences of AESIs from the first dose of any IP until the 12-month follow-up (Day 388)
- Incidences of clinical laboratory abnormalities

No hypothesis testing is planned for any of the safety endpoints.

### 2.3.2.2 Secondary Pharmacokinetic Endpoints

For each antibiotic, to determine if the single-dose PK parameters are affected by AV7909 vaccination, the equivalence tests will be performed in the similar manner as those performed for the primary PK analyses.

Specifically, for each antibiotic, the null hypotheses are:

- $AUC_{0-12h}$ : Geometric mean of within-participant ratios of post-vaccination (Day 31 for ciprofloxacin and Day 32 for doxycycline) over the pre-vaccination (Day 4 for ciprofloxacin and Day 2 for doxycycline)  $AUC_{0-12h}$  is greater than 1.25 or less than 0.80.
- $C_{max}$ : Geometric mean of within-participant ratios of post-vaccination (Day 31 for ciprofloxacin and Day 32 for doxycycline) over the pre-vaccination (Day 4 for ciprofloxacin and Day 2 for doxycycline)  $C_{max}$  is greater than 1.25 or less than 0.80.

No hypothesis testing is planned for the secondary PK endpoints, which will be evaluated and reported for information only.

### 2.3.2.3 Secondary Immunogenicity Endpoints

For each antibiotic, to evaluate whether the co-administration of the antibiotic affects the immune response after two IM doses of AV7909, a non-inferiority test will be conducted.

Specifically, the null hypotheses are:

- For ciprofloxacin: the geometric mean ratio of TNA  $NF_{50}$  values at Day 37 for Group 1 over Group 3 is less than or equal to 0.5

- For doxycycline: the geometric mean ratio of TNA NF50 values at Day 37 for Group 2 over Group 3 is less than or equal to 0.5

The null hypothesis is rejected when the lower bound of the two-sided 95% CI of the geometric mean ratio of TNA NF50 values is greater than 0.5.

For each antibiotic, the formal hypothesis testing for the secondary immunogenicity endpoints will only be carried out after the primary PK endpoint has been met for the corresponding antibiotic. If the primary PK endpoint for an antibiotic is not met, the corresponding secondary immunogenicity endpoints will be provided for information only.

## 2.4 Sample Size and Power Considerations

The sample size for this study was selected based on both the primary and secondary endpoints.

Assessment as to whether vaccination with AV7909 affects the PK of either ciprofloxacin or doxycycline will be made based on the geometric mean of the within-participant ratios (post-vaccination over pre-vaccination) of AUC0-12h and Cmax. The equivalence margin for the geometric mean ratio is [0.80, 1.25], which will be compared with the 90% confidence interval (CI) for the geometric mean of with-participant ratios of AUC0-12h and Cmax. Assuming the coefficient of variation (CV) is 30% for the geometric mean ratio and the true geometric mean ratio is 0.95, 27 participants allow for 90% power to reject the null hypothesis at a significance level of 5%. A group size of 40 participants for Group 1A (AV7909 + ciprofloxacin with PK) or Group 2A (AV7909 + doxycycline with PK) is planned to allow for up to 30% of participants being excluded from the PK Population.

A sample size of 53 in each of the IP groups (Group 1 = AV7909 + ciprofloxacin, Group 2 = AV7909 + doxycycline, and Group 3 = AV7909 only) provides 90% power at 2.5% one-sided significance level for the non-inferiority test, defined as the lower bound of the two-sided 95% CI of the geometric mean ratio of the AV7909 + antibiotic over AV7909 only (Group 1 vs. Group 3, Group 2 vs. Group 3) greater than 0.5. This assumes that the true ratio of the geometric means between two groups is 0.85 and the CV of TNA NF50 values in each group is 100%. A total of 70 per IP group is planned to allow for up to 25% of drop-out rate.

## 2.5 Randomization and Blinding

### 2.5.1 Randomization

At the Randomization visit (Day 1), after the PI has confirmed that the participant meets all the inclusion criteria and none of the exclusion criteria, a central randomization process will be used to assign each participant to one of the three open-label IP groups with the ratio of 1:1:1 (block size of 3). Approximately the first 40 participants who are randomized into IP Groups 1 and 2 will be assigned to Treatment Groups 1A or 2A while the remaining 30 participants randomized into IP Groups 1 and 2 thereafter will be assigned to Treatment Groups 1B or 2B.

Randomization will be stratified by site. The sites will be asked to the extent possible to execute a recruitment process that achieves a representative racial/ethnic distribution in populations that are reasonably gender- and age-balanced (i.e., at least 40% male with 40% of participants in the two age ranges of 18 to 30 years of age and 31 to 45 years of age).

A randomization plan will be prepared and finalized prior to randomization of the first participant. The specific instructions for randomizing participants will be provided in the Pharmacy Manual.

A screen failure is a participant from whom informed consent is obtained and documented in writing, but who is not subsequently randomized to study treatment. Reasons for screen failure are to be recorded on the electronic case report forms (eCRFs).

Participants who are screen failures are permitted to be rescreened one time (only) according to the PI's discretion. If a participant is rescreened, a new subject ID will be assigned. To link records to the same participant, the participant's previous subject ID will be recorded in the eCRF along with the new subject ID. Participants who complete the rescreening and are randomized in the study will not be considered as screen failures.

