5. STUDY POPULATION

Participants will be recruited at up to five clinical research centers in the United States. At least 210 healthy adults meeting the eligibility criteria will be randomized 1:1:1 to one of the three IP groups: 70 in Group 1 (AV7909 + ciprofloxacin), 70 in Group 2 (AV7909 + doxycycline) and 70 in Group 3 (AV7909 alone). Groups 1 and 2 will each have two subgroups; the A subgroup (N=40) will undergo PK sessions while the B subgroup (N = 30) will not. Approximately the first 40 participants who are randomized into Groups 1 and 2 will be assigned to Treatment Group 1A or Group 2A, while those who are randomized into Groups 1 and 2 thereafter will be assigned to Groups 1B or 2B.

No waivers of inclusion and/or exclusion criteria will be permitted in the trial. The sites will be asked to implement procedures that will ensure a representative racial distribution among recruited participants and result in populations that are gender- and age-balanced (ie, between 40-60% male with 40-60% of participants in the two age ranges of 18-30 years of age and 31-45 years of age).

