6.3. Measures to Minimize Bias

6.3.1. Method of Treatment Assignment

After the ICF has been signed and dated by the participant and PI/designee but before any screening procedures are performed, the participant will be assigned a unique subject identification (ID) number by the site. To maintain confidentiality, the subject ID will be used to identify the participant for data collected in eCRFs throughout the trial and for all clinical laboratory samples. The investigational site will retain a master list linking the subject ID with the name, date of birth, and contact information of the participant. The master list is to be retained by the site only and is not to be collected by Emergent or its agents.

If a participant is rescreened, a new subject ID will be assigned. To link records to the same participant, the participant's previous subject ID will be recorded in the eCRF along with the new subject ID.

At the Randomization visit (Day 1), after the PI has confirmed that the participant meets all the inclusion criteria and none of the exclusion criteria, a central randomization process will be used to assign each participant to one of the three open-label IP groups. The sites will be asked to the extent possible to execute a recruitment process that achieves a representative racial/ethnic distribution in populations that are reasonably gender- and age-balanced (ie, at least 40% male with 40% of participants in the two age ranges of 18-30 years of age and 31-45 years of age).

A randomization plan will be prepared and finalized prior to randomization of the first participant. The specific instructions for randomizing participants will be provided in the Pharmacy Manual.

If a participant signs and dates the ICF but is not randomized within the screening period window, that participant is considered a screen failure unless he or she signs a new ICF, is re-screened and is randomized within the allowable window (refer to [Section 5.4](#)).

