6.3.2. Blinding

Not applicable; this is an open-label study.

AV7909 Anthrax Vaccine

IND 014451

Protocol EBS.AVA.210, Version 3.0 (28 October 2019)

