### 3.3 Multicenter Study

This study is expected to enroll 210 participants at approximately 4 sites in the United States. Subject randomization and protocol deviations will be summarized by site and treatment group.

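### A single fixed block size of 3, within site and open label, lets anyone who knows or infers it foresee every third allocation; randomly varying blocks would be a cheap improvement

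*SAP*

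**What the plan says.** SAP 2.5.1 (Randomization) allocates participants to the three groups "with the ratio of 1:1:1 (block size of 3"). SAP 2.2.1 adds that "Randomization will be stratified by site", so the blocks run within site. On blinding, Protocol 6.3.2 says "Not applicable; this is an open-label study", and SAP 2.5.2 agrees.

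Protocol 6.3.1 (Method of Treatment Assignment) says "a central randomization process will be used to assign each participant to one of the three open-label IP groups". It gives no block size and points to a separate document: "A randomization plan will be prepared and finalized prior to randomization of the first participant". That document is not part of the protocol or SAP. Neither the protocol nor the SAP mentions varying block sizes, and neither says whether sites could see the SAP during enrolment.

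On size, the SAP says "This study is expected to enroll 210 participants at approximately 4 sites in the United States" (section 3.3), and the protocol says "Participants will be recruited at up to five clinical research centers in the United States" (section 5).

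**The concern.** With three arms at 1:1:1, a block of 3 holds each arm exactly once. Because treatment is open, staff see every past allocation at their site. Once two in a block are known, the third is fixed. Central randomization hides the list but cannot prevent that deduction.

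The protocol supplies ordinary, innocent reasons to care which group comes next:

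- **Visits.** The synopsis gives 19 clinic visits in Group 2A, 17 in 1A and 6 in the other groups.
- **Timing.** Group 2A is admitted on the evening of randomization (Protocol 8.1.1.2).
- **Restrictions.** The antibiotic groups carry contraception, diet, sun and drug restrictions (Protocol 5.1, 5.3 and 6.5.1).

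There is also room to act on it. Screening runs from Day -28 to Day -2, so sites can order the Day 1 visits, and exclusion 23 rests on investigator opinion.

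At stake is the comparability of Groups 1 and 2 with Group 3 in the TNA non-inferiority test (SAP 7.2) and in the safety summaries. An objective assay protects against biased reading of the result. It does not protect against biased entry into a group.

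**Working it through.** **1. The plan's own figure.** Inputs from SAP 2.4: CV 100%, true ratio 0.85, margin 0.5, one-sided 2.5%, 90% power.

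- Log-scale SD = sqrt(ln(1 + 1²)) = 0.833.
- Distance to the margin = ln(0.85/0.5) = 0.531.
- 53 per group gives 90.2% power (noncentral t), which agrees with the SAP.
- 53/0.75 = 70.7, against the plan's 70: "A total of 70 per IP group is planned to allow for up to 25% of drop-out rate". The difference is rounding.
- 210/3 = 70 complete blocks, hence 70 per group.

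The sample size is not in question.

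**2. Predictability with blocks of 3.** The chance of a correct best guess is 1/3 at the first position, 1/2 at the second and 1 at the third.

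- Overall: (1/3 + 1/2 + 1)/3 = 11/18 = 61.1%, against 33.3% without blocking.
- Certain: 1/3 of allocations. Allowing for incomplete last blocks, this is 68 to 70 of 210 at 4 sites and 67 to 70 at 5.

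**3. The phase with unequal visits.** About 40 in each antibiotic arm go to 1A or 2A. With 40 in Group 3 alongside them, that is roughly the first 120 randomizations, so 120/3 = 40 of the certain allocations. In the remaining 90 or so, all groups have 6 visits and differ only in antibiotic dosing and its restrictions.

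**4. Inferring the block size.** Suppose a site sees its first triples each contain all three arms.

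- Under simple randomization, each triple does so with probability 6/27, so three in a row has probability (6/27)³ = 1.1%, and four 0.24%.
- Under blocks of 6, the chance is 8/20 = 40% per block (two triples): 16% after four triples and 6.4% after six.

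Telling 3 from 6 therefore takes a little longer, but a site of 42 to 53 participants has 14 to 17 blocks.

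**5. Alternatives.** Fixed sizes are by exact enumeration. Varying sizes are simulated (600 runs, 52 participants per site), with an observer who knows the possible sizes but not their order.

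| Blocks | Certain | Best guess correct |
|---|---|---|
| Fixed 3 | 33.3% | 61.1% |
| Fixed 6 | 20.0% | 56.1% |
| Fixed 9 | 14.3% | 53.2% |
| Varying 3/6 | about 8% | about 57% |
| Varying 6/9 | about 5% | about 54% |
| No restriction | 0% | 33.3% |

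**6. What it would take to move the result (illustration).** Assume steering acts only at the certain allocations, one third of each arm, and shifts mean log TNA there by d in opposite directions in the two arms. The bias in the log ratio is then 2d/3.

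- For a true ratio of 0.5 to look like 0.85: 2d/3 = 0.531, so d = 0.80, or 0.80/0.833 = 0.96 SD. The test would then pass falsely about 90% of the time.
- Smaller shifts still matter at the margin. With d = 0.2 (0.24 SD) the bias is 0.133. The standard error is 0.833 × sqrt(2/53) = 0.162, and the false-pass rate rises from 2.5% to about 13%.

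**The case against.** The other side has four good points.

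- **Disclosure.** Only the SAP prints the block size, and it need only be final before database lock. A reader might infer that sites were told the block size; nothing in the documents says so. What stands is the weaker statement that it can be worked out.
- **Motive.** A reader might apply the 17 to 19 against 6 visit contrast to all 70 or so certain allocations. It covers only about 40, because Groups 1B, 2B and 3 all have 6 visits.
- **Endpoints.** The primary PK tests compare each participant with himself or herself (Protocol 10.1.1, SAP 6.5.1). Selection between arms does not bias them directly. The exposed formal test is secondary and is run only if the PK endpoint is met for that antibiotic.
- **Safeguards.** It would be wrong to say there are none. SAP 7.2.1 prespecifies an exploratory model with site, sex and age, and requires differences from the unadjusted result to be discussed in the report. Prior anthrax vaccination is excluded, a Day 1 TNA at or above the detection limit removes a participant from the Immunogenicity Population, eligibility waivers are barred, and reasons for screen failure are recorded.

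In addition, staff would be choosing among unvaccinated healthy adults before any response exists, and choosing people who tolerate more visits need not select on TNA response.

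These points narrow the concern but do not remove it. The exploratory model does not govern the non-inferiority conclusion and cannot correct for unmeasured selection, and central allocation does not hide a third position that follows from the first two.

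**Conclusion.** The point holds as a weakness of the allocation method. About 70 of 210 allocations can be foreknown and 61% can be guessed, provided that someone at the site knows or infers the block size and keeps track. The randomization plan was not available for this review. If it already sets varying blocks, SAP 2.5.1 is what needs correcting.

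The documents do not support the stronger reading that the trial's results are biased. Predictability is shown, and selection is not. A false non-inferiority conclusion becomes likely only with substantial selection (about one SD at every certain allocation, under the assumptions above), although smaller selection would raise the error rate if the true ratio lay at the margin. The primary PK conclusions stand apart from this. The point is best classed as a cheap improvement.

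**What to change.** In SAP 2.5.1 and the randomization plan, replace the fixed block of 3 with permuted blocks of randomly varying size within site, for example 6 and 9, and keep the sizes out of any document that sites can see. Certain allocations fall from 33% to about 5%, roughly 10 of 210. Best-guess accuracy falls less, from 61% to about 54%, so the gain is mainly the loss of certainty. If enrolment has begun, apply the change to the unused part of the list. If enrolment is complete, state the limitation in the study report and compare baseline characteristics by group at predictable and unpredictable block positions.

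The cost is regenerating the central list and accepting slightly looser balance within a site at any moment. Sample size, endpoints and visit procedures do not change.
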